Participants will be assigned to attention control training or the comparison stimuli computer task in a double-blind randomized control trial design. Both computerized dot probe tasks display two stimuli on a computer screen, one above the other, followed by a small right or left arrow appearing in the location vacated by one of the faces (see figure below). Participants are required to respond as quickly as they can by pressing the indicated right or left arrow on their computer keyboard without compromising accuracy.

In all trials, attention control training will present one neutral and one threatening stimulus on the screen. In most aspects of the study, the stimuli will be pictures of facial expressions. Specifically, in attention training, the participant will view one neutral face and one angry face on the screen at the same time. In the comparison condition, the

stimuli will always be two neutral faces presented before responding to the arrow.

Our investigational intervention = Attention Control Training will consist of:

- 6 sessions lasting approximately 10 minutes each.
- Each session will consist of 128 presentations of pairs of neutral and threatening stimuli, followed by the presentation of a response cue (right or left arrow to be clicked on a computer keyboard).
- Ideally participants will complete 2 sessions per week, allowing them to complete the trial in less than one month's time

Our comparison task will consist of:

- 6 sessions of a presumably inactive neutral-neutral intervention lasting approximately 10 minutes each.
- Each session will consist of 128 presentations of pairs of faces, followed by the presentation of a response cue (right or left arrow to be clicked on a computer keyboard).
- Ideally participants will complete 2 sessions per week, allowing them to complete the trial in less than one month's time.

IMPORTANTLY, after completing this inactive intervention and post assessment, all of these participants whose PTSD symptoms have not improved will be invited to return for a full trial of attention control training as described above to mitigate any concerns about a theoretically inactive intervention.

Aims for Clinical Trials

The major aims of the trials are straightforward:

- (1) Evaluate whether attention control training (ACT) is an effective therapy for reducing PTSD symptoms in combat veterans and/or women who have experienced interpersonal violence in comparison to a presumably inactive computer task.

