- (2) Evaluate whether ACT is an effective therapy for reducing associated symptoms of PTSD including anxiety, depression, emotion regulation difficulties, and substance use in comparison to a presumably inactive computer task in individuals with PTSD.
- (3) Compare the effectiveness of an online version of ACT delivered at a distance compared to in the clinic as well as a presumably inactive computer task for combat veterans with PTSD.

This study will be entered on ClinicalTrials.gov to formally register the project. We will add study number once approved by the registry.

Study Participants

Study 1: Recent combat veterans with symptoms of PTSD.

- We have a goal to recruit 100 veterans and active duty personnel serving in the U.S. Military since March 20, 2003 as potential participants for this aspect of the study.
- This sample will be randomly assigned to one of three study arms:
 - Attention control training at the clinic using faces as stimuli
 - Attention control training at the veteran's home via the internet using faces as stimuli
 - Comparison neutral-neutral task at the clinic using faces as stimuli
- Combat veterans with PTSD will be recruited from the community.
- Advertising on TV, with university veteran groups, with Lutheran Family Services, and from other groups serving veterans.

Study 2: Women exposed to interpersonal violence with symptoms of PTSD.

- Attention control training versus comparison task with a total of 60 women who have been exposed to interpersonal violence.
- We will use the faces version of the task with women.
- Participants will be randomly assigned to study condition.
- For safety, we will only include women who are not living with their abuser.
- We will ask about current safety before every session.
- Recruitment and sessions will occur at the Women's Center for Advancement (WCA) or at Creighton University if community women call to participate.

Measures

Demographics. All participants will answer standard demographic questions including age, gender, years of education, and marital status.

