Alcohol Use Disorders Identification Test (AUDIT; Saunders, Aasland, Babor, de la Fuente, & Grant, 1993). The AUDIT is a brief 10-item questionnaire that was developed to measure severity of hazardous or harmful alcohol consumption. Utilizing a 5-point Likert scale, the measure includes questions pertaining to amount and frequency of drinking, symptoms of alcohol dependence, and alcohol-related problems. Example items include "How often during the last year have you been unable to remember what happened the night before because of your drinking?" Higher scores are indicative of more severe alcohol use. The AUDIT has evidenced strong reliability including internal consistency and test-retest reliability, as well as construct validity across a variety of clinical and non-clinical samples (Reinert & Allen, 2002; 2007).

Beck Anxiety Inventory (BAI; Beck, Epstein, Brown, & Steer, 1988). The BAI is a 21-item questionnaire designed to measure common anxiety symptoms across somatic and subjective factors. Participants rate to what degree they have experienced items such as "feeling hot", "numbness or tingling", and "fear of the worst happening" in the last month. Responses occur on a 4-point Likert scale, ranging from 0 (*not at all*) to 3 (*severely-it bothered me a lot*). Total scores range from 0 to 63 with higher values indicative of more severe anxiety symptoms. The BAI is a commonly used measure of anxiety. A recent meta-analysis examining the psychometric properties of the BAI reported high internal consistency and good test-retest reliability. Convergent validity is strong with typically large correlations between the BAI and other indices of anxiety (Bardhoshi, Duncan, & Erford, 2016)

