Clinician Administered PTSD Scale for DSM-5 (CAPS-5; Weathers et al., 2017). The CAPS-5 is a 30-item, structured interview designed to fully assess PTSD, consistent with the DSM-5. Specifically, the CAPS-5 provides the clinician standardized questions and probes, and enables a determination of the participant's diagnostic status, symptom characteristics, and symptom severity. It takes approximately 45-60 minutes, and will be administered only by trained researchers who are supervised by PhD-level psychologists or the by the psychologists themselves. The CAPS is considered the gold standard for PTSD assessment. Previous versions have shown impressive reliability and validity (e.g., Blake et al., 1995). Modified to adhere to DSM-5 changes, the CAPS-5 shows psychometric properties consistent with its predecessor. PTSD diagnosis and symptom severity scores have shown strong inter-rater and test-retest reliability, as well as high internal consistency and convergent validity with the CAPS for DSM-IV (Weathers et al., 2017).

Deployment Risk and Resilience Inventory-2 (DRRI-2) Combat Exposure Scale (Vogt et al., 2013). This 17 item scale measures combat-related circumstances during deployment such as firing a weapon, being fired on, being attacked or witnessing an attack (e.g., encountering an explosive device), encountering friendly fire, and going on special missions and patrols that involve such experiences. This war-zone factor refers to objective events and circumstances and does not include personal interpretations or subjective judgments of the events or circumstances. Participants rate items such as "I personally witnessed someone from my unit or an ally unit being seriously wounded or killed." On a 6-point Likert scale ranging from (1 = "Never" to 6 = "Daily or almost daily").

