Difficulties in Emotion Regulation Scale -16 (DERS-16; Bjureberg et al., 2016). Comprised of 16 items, the DERS-16 provides a brief, yet comprehensive measure of emotion regulation abilities. The DERS-16 assesses five of the original six domains of emotion regulation including, for example, lack of emotional clarity, difficulty controlling impulsive behaviors when distressed, and limited access to emotion regulations strategies perceived as effective. Participants rate items such as "I have difficulty making sense out of my feelings" and "When I am upset, I become out of control" on a 5-point Likert scale (1=*almost never*; 5=*almost always*). The brief measure evidenced strong internal consistency, good test-retest reliability, as well as good convergent and discriminant validity in clinical and community samples. In addition, there were minimal differences in validity between the DERS-16 and the original, 36-item DERS (Bjureberg et al., 2016).

Drug Abuse Screening Test – 10 (DAST-10; Bohn, Babor, & Kranzler, 1991; Skinner, 1982). The DAST-10 is designed to provide a brief, self-report measure of substance abuse in the last 12 months. Specifically, participants are asked to consider their use of drugs such as cannabis, cocaine, hallucinogens, and narcotics, while excluding their use of alcohol and tobacco. Composed of 10-items, participants respond 'yes' or 'no' to questions such as "Have you ever experienced withdrawal symptoms (felt sick) when you stopped taking drugs?" and "Have you neglected your family because of your use of drugs?" DAST-10 scores range from 0 to 10 with higher scores indicative of more severe drug abuse. The DAST is a widely-used measure of substance abuse with sound psychometric properties. The DAST-10, specifically, has shown high internal consistency, adequate test-retest validity, and convergent and divergent validity with appropriate measures (Yudko, Lozhkina, & Fouts, 2007).

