We will conduct a series of standard analyses. For example, we will calculate summative scores for participant questionnaire responses. In addition, we will conduct Repeated Measures Analyses of Variance, t-tests, correlation, and multiple regression analyses on these summative questionnaire scores as well as on the reaction time and accuracy data that we collect during the treatment trials and the pre- and post-training measures.

Anticipated Risks and Mitigation of Risks

We recognize that participating in the assessments required by the study may cause some psychological discomfort to our participants. As a result we regard this project as

having greater than minimal risk. We expect psychological discomfort when participants talk about their traumatic experiences and symptoms during the structured interview or answer questions about these experiences on questionnaires. Psychological assessments will be conducted by trained mental health professionals who are able to recognize any serious exacerbations of symptoms and provide appropriate immediate interventions and referrals.

Specifically, if participants report significant suicidal or violent intent or significant worsening of their symptoms, referrals will be made to [name], MS LMHP, Director of At Ease with Lutheran Family Services in Bellevue NE for the veterans through their partnership with At Ease USA, and for the women through the partnership that At Ease USA has with the WCA. If such referrals are warranted, participation in the trials will be discontinued.

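### The plan fixes neither the model nor the PTSD scale for the treatment comparison; adjusting Session 8 for Session 1 would be more efficient than the change-score or Session 8-only tests it allows.

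*Combined protocol and SAP*

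**What the plan says.** In the combined protocol and SAP, Proposed Analyses consists of a statement that questionnaire items will be summed, followed by the commitment that "we will conduct Repeated Measures Analyses of Variance, t-tests, correlation, and multiple regression analyses on these summative questionnaire scores", and on the reaction-time and accuracy data. It names no primary outcome, between-arm contrast, covariate or significance level.

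Aims for Clinical Trials, Aim 1, concerns "reducing PTSD symptoms in combat veterans and/or women who have experienced interpersonal violence", compared with a presumably inactive computer task. It names no instrument. Aim 2 covers "anxiety, depression, emotion regulation difficulties, and substance use". Aim 3 is to "Compare the effectiveness of an online version of ACT delivered at a distance compared to in the clinic" and with the inactive task.

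Study Participants gives a recruitment goal of 100 for Study 1, where "This sample will be randomly assigned to one of three study arms" (ACT in the clinic, ACT at home, neutral task in the clinic), and 60 women in two conditions for Study 2. No allocation ratio is given.

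Two PTSD severity scales, CAPS-5 and PCL-5, are given at both Session 1 and Session 8 (Step by Step Procedures). Measures says that "The CAPS is considered the gold standard for PTSD assessment", which describes the instrument but does not make it the deciding outcome. CAPS-5 is the past-month version at Session 1 and the past-week version at Session 8.

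**The concern.** Four methods are listed and none is assigned to the treatment comparison. Several natural readings leave information unused. A group-by-time test from repeated measures ANOVA works on change from Session 1, and a plain t-test may use change or Session 8 scores alone. The listed multiple regression avoids the loss only if the Session 1 score is a covariate, which the text does not say.

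The arms are small, so the loss matters, and the Session 1 scores needed to avoid it are already collected. The CAPS-5 recall window also changes between sessions. Raw change, and any within-arm pre/post test, therefore mixes a one-month with a one-week window.

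With two PTSD scales and neither named as deciding, the scale that supports ACT could be chosen after the data are seen. Under Potential Direct and Societal Benefits, the sponsor is ready to offer ACT as therapy if it is shown to be effective. What counts as effective should therefore be fixed beforehand.

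**Working it through.** **Figure to reproduce.** None: the documents contain no power or sample-size calculation.

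**Inputs from the documents.** Study 1: 100 in three arms, 100/3 = about 33 per arm. Study 2: 60 in two arms, 60/2 = 30 per arm. One assessment before training and one after.

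**Assumptions, because the documents are silent.** Equal allocation, recruitment goals met, no dropout, two-sided 5%, true effect of 0.5 SD (Session 8 SD), equal Session 1 and Session 8 SDs (relaxed below), baseline–post correlation r from 0.4 to 0.7.

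**What each test analyses.** With one pre and one post score, the two-arm group-by-time test is the t-test on change. In three-arm Study 1 it is a 2-df test, equal to one-way ANOVA on change, and does not by itself say which arm differs. In units of the Session 8 variance, the error variances are:

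- change: 2(1 − r)
- Session 8 alone: 1
- Session 8 adjusted for Session 1: 1 − r²

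The ratio of adjusted to change is (1 − r²)/[2(1 − r)] = (1 + r)/2, which is below 1 for every r < 1. The ratio of adjusted to Session 8 alone is 1 − r².

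**Power.** Noncentral t with noncentrality 0.5/[s·√(2/n)], where s is the square root of the variance above. Degrees of freedom are 2n − 2, less one for the covariate. Example, n = 33 and r = 0.5, with √(2/33) = 0.246: change has s = 1 and noncentrality 2.03, giving 51.6%; adjusted has s = √0.75 = 0.866 and noncentrality 2.35, giving 63.7%.

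| n per arm | r | Change | Session 8 alone | Adjusted |
|---|---|---|---|---|
| 33 | 0.4 | 44.7% | 51.6% | 58.8% |
| 33 | 0.5 | 51.6% | 51.6% | 63.7% |
| 33 | 0.6 | 60.9% | 51.6% | 70.5% |
| 33 | 0.7 | 73.3% | 51.6% | 80.0% |
| 30 | 0.4 | 41.2% | 47.8% | 54.7% |
| 30 | 0.5 | 47.8% | 47.8% | 59.4% |
| 30 | 0.6 | 56.7% | 47.8% | 66.3% |
| 30 | 0.7 | 69.1% | 47.8% | 76.0% |

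**Unequal SDs.** Let k be the Session 8 SD divided by the Session 1 SD. The change variance becomes 1 + 1/k² − 2r/k; the adjusted variance stays 1 − r². At r = 0.5 and 33 per arm:

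| k | Change variance | Change | Adjusted | Gain |
|---|---|---|---|---|
| 0.8 | 1.3125 | 41.5% | 63.7% | 22 points |
| 1.0 | 1.0000 | 51.6% | 63.7% | 12 points |
| 1.2 | 0.8611 | 57.8% | 63.7% | 6 points |

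**Which Study 1 contrast.** If Aim 1 is read as both ACT arms pooled against neutral (67 vs 33), with the same 0.5 SD effect in each and r = 0.5, the standard-error factor is √(1/67 + 1/33) = 0.213. Power is 64% on change and 77% adjusted, against 52% and 64% for one ACT arm.

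**Either scale counting.** On one contrast, the chance that at least one of two scales falsely favours ACT at one-sided 2.5% is 1 − Φ₂(1.96, 1.96; ρ), where Φ₂ is the bivariate normal distribution function. This gives 4.5% at scale correlation ρ = 0.5 and 3.9% at ρ = 0.8. The correlation is assumed.

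**The case against.** The strongest reply is that nothing listed is wrong. Change-score and Session 8-only comparisons are valid in a randomised trial, and multiple regression may already be meant to carry the baseline score. That stands: the loss depends on a choice that the plan has not made.

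The size of the gain also rests on assumptions. Equal SDs are doubtful for CAPS-5, because its recall window changes. If the Session 8 SD is 1.2 times the Session 1 SD and r = 0.7, the gain over change at 33 per arm is about 1 point (78.6% vs 80.0%). That stands too, which is why the gain is shown over a range of SD ratios.

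A third reply is that clinic ACT against neutral is not the only reading of Aim 1, which does not restrict ACT to the clinic. Pooling the ACT arms is equally natural and raises power about as much as adjustment does. This is correct, so the choice belongs to the sponsor.

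Two stronger readings should be resisted. A reader might infer that the trial falls short of a planned power of 59–80%; no power is planned anywhere, and that range is only the adjusted-model figure under the assumptions above. A reader might also infer that PCL-5 should give way because its one-month window overlaps training; BAI has the same window under Measures, so this does not separate them. The case for CAPS-5 is the protocol's own description of it.

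**Conclusion.** The concern holds as a gap in pre-specification and efficiency. It does not show an invalid analysis. Proposed Analyses commits to no model for the treatment comparison, and no section says which PTSD scale decides Aim 1.

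Under the stated assumptions, with r from 0.4 to 0.7, pairwise power is 45–73% on change, 52% on Session 8 alone and 59–80% adjusted at 33 per arm. At 30 per arm it is 41–69%, 48% and 55–76%. Against change, adjustment gains 14 points at r = 0.4 and 7 at r = 0.7 (33 per arm, equal SDs). Against Session 8 alone it gains 7 to 28 points. The direction for equal SDs needs no effect-size assumption; the size does.

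Leaving the scale open is worth about 1.4 to 2.0 percentage points of extra false-positive risk per contrast (3.9 − 2.5 and 4.5 − 2.5). The change in CAPS-5 recall window is a separate reason not to report raw change. The between-arm comparison of change remains valid, because both arms share the mismatch, but a within-arm change cannot be read as improvement on one scale. A baseline covariate needs no common metric.

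**What to change.** - **Model and scale.** In each study, state that the treatment comparison is a regression of Session 8 CAPS-5 total severity on assigned arm and Session 1 CAPS-5 severity. Treat PCL-5 as supportive, and do not use raw CAPS-5 change as the effect estimate.
- **Study 1 contrast.** Fit one three-arm model. Before analysis, the sponsor names the Aim 1 contrast: clinic ACT against neutral, or both ACT arms pooled against neutral. Report the other contrasts, including online against clinic ACT for Aim 3, from the same model with 95% confidence intervals.
- **Aim 2.** Use the same baseline-adjusted model for the Aim 2 scales.

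The cost is analysis-plan wording; no new data, visits or participants are needed. The one real concession is that a significant PCL-5 result alongside a null CAPS-5 result could no longer be claimed as meeting Aim 1. If the sponsor already intends a baseline-adjusted regression, writing it down costs nothing.

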- *Demographics*
- *Alcohol Use Disorders Identification Test*
- *Beck Anxiety Inventory*
- *Difficulties in Emotion Regulation Scale -16*
- *Drug Abuse Screening Test – 10*
- *Patient Health Questionnaire*

- *PTSD Checklist for DSM-5*
- *Threat-Related Attention Bias and Attention Bias Variability*

Participants who give consent and meet the study inclusion criteria but not exclusion criteria, will be randomly assigned to either attention control training or the comparison task in a double blind fashion. Those participants assigned to the neutral-neutral comparison condition will be given the opportunity to participate in ACT training immediately after completing session 8 if they are interested. They can participate in ACT in the clinic or from home online, so all participants will have an opportunity to receive the target intervention. If individuals participate in ACT after completing their participation in the neutral condition of the trial, we will ask them to complete the PCL-5 to assess PTSD symptoms at the end of their ACT training (either in the clinic or online through Qualtrics, Creighton University's online survey platform).

Sessions 2-7: Participants will complete short appointments for their computer attention training or comparison task session. Ideally participants will complete two training sessions per week, such that their participation from start to finish will complete in one month's time.

- For Study 1 sessions will occur in a private room at the Creighton University Psychology Department or online from the participants' personally selected private space (we are encouraging a quiet room in their home). For those participants completing training online, they will be asked to contact study investigators just before starting the task, to offer a relationship aspect to the online delivery and ensure they are conducting their training in a private setting.
- For Study 2 sessions will occur at the WCA or at Creighton University in a private room.

Session 8: Participants will return for a final appointment following training completion, and be reassessed with the same questionnaires and CAPS interview that were employed during the pretreatment assessment. (See the list below for post-intervention questionnaires.) The demographic, trauma screens, and M.I.N.I will be not readministered.

- *Clinician Administered PTSD Scale for DSM-5* (past week version)
- *Alcohol Use Disorders Identification Test*
- *Beck Anxiety Inventory*

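### Minor: referral for worsening ends trial participation with no exit assessment, so the few people who worsen during training may have no post-treatment score

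*Combined protocol and SAP*

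**What the plan says.** The rule is in the combined protocol and SAP under Anticipated Risks and Mitigation of Risks: "if participants report significant suicidal or violent intent or significant worsening of their symptoms, referrals will be made", and then "If such referrals are warranted, participation in the trials will be discontinued". It comes straight after a statement about the assessments: "Psychological assessments will be conducted by trained mental health professionals who are able to recognize any serious exacerbations of symptoms".

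Step by Step Procedures fixes when outcomes are collected. For Sessions 2-7, "Participants will complete short appointments for their computer attention training or comparison task session"; no symptom measure is listed. For Session 8, "Participants will return for a final appointment following training completion"; the CAPS-5, PCL-5 and other scales are repeated there. Study 2 adds a check on the women's safety: "We will ask about current safety before every session". Online participants in Study 1 get in touch with staff before each task.

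Withdrawal is mentioned only in connection with payment. The PCL-5 contacts at 6 and 12 months are counted from study completion, which is not defined for someone stopped early. Proposed Analyses names repeated measures ANOVA, t-tests, correlation and regression, but no analysis set and no method for missing data.

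**The concern.** Symptom worsening is the adverse direction of the trial's main outcome. If a participant leaves because of it and is not measured again, missingness depends on the outcome. A pre/post ANOVA or a t-test on change needs both values, so unless something else is specified these people drop out of the comparison.

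Three things could follow. Within-arm improvement would look somewhat larger than it was. A true ACT benefit would be diluted, because the comparison arm would lose more of its poor outcomes. If ACT made some people worse, part of that harm would go unseen. Scores that were never collected cannot be recovered at the analysis stage.

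**Working it through.** **What the text implies**

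- Worsening found at Session 1 precedes randomisation, and worsening found at Session 8 surfaces while the outcome is being recorded. Only Sessions 2-7 are exposed.
- The document uses the word trial in two senses. One is the course of training: "will be invited to return for a full trial of attention control training as described above". The other is the study: "after completing their participation in the neutral condition of the trial". The section headed Aims for Clinical Trials also uses the plural for the studies. The study reading is the more natural one, and nothing says that stopped participants are kept for assessment.

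**Size**

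The plan gives no SD, effect size or discontinuation rate, so there is no figure to reproduce. Only the sample sizes come from the documents (100 in three arms; 60 in two). All other inputs are assumptions:

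- Change is normal with SD s = 10; mean μ = 0 (comparison) and -5 (ACT); higher is worse.
- A share d of those worsening by c or more is detected before Session 8 and lost.
- Allocation is equal: about 33 per arm in Study 1 (33 comparison, 67 ACT over two arms) and 30 per arm in Study 2.

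With z = (c - μ)/s, the observed arm mean is

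[Φ(z)·E(X|X<c) + (1-d)(1-Φ(z))·E(X|X≥c)] / [Φ(z) + (1-d)(1-Φ(z))].

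Worked case, c = 10 and d = 0.25:

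- Comparison, z = 1: [0.8413 × (-2.876) + 0.75 × 0.1587 × 15.251] / [0.8413 + 0.1190] = -0.605/0.9603 = -0.63.
- ACT, z = 1.5: [0.9332 × (-6.388) + 0.75 × 0.0668 × 14.387] / [0.9332 + 0.0501] = -5.240/0.9833 = -5.33.
- Difference: -5.33 + 0.63 = -4.70, against a true -5.

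| c | d | Comparison | ACT | Difference | Attenuation | Lost, Study 1 | Lost, Study 2 |
|---|---|---|---|---|---|---|---|
| 10 | 0.10 | -0.25 | -5.13 | -4.88 | 2.3% | 1.0 | 0.7 |
| 10 | 0.25 | -0.63 | -5.33 | -4.70 | 6.0% | 2.4 | 1.7 |
| 10 | 1.00 | -2.88 | -6.39 | -3.51 | 29.8% | 9.7 | 6.8 |
| 5 | 0.10 / 0.25 | | | -4.88 / -4.68 | 2.3% / 6.5% | 2.1 / 5.2 | 1.4 / 3.5 |
| 15 | 0.10 / 0.25 | | | -4.92 / -4.81 | 1.5% / 3.9% | 0.4 / 0.9 | 0.3 / 0.7 |

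The row with d = 1 is an extreme; with no symptom scale in Sessions 2-7 it is not a realistic case.

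- **Against sampling error.** The standard error is 10√(2/33) = 2.46, or 10√(2/30) = 2.58. At c = 10 the attenuation of 0.12-0.30 points is 0.12/2.46 = 5% to 0.30/2.46 = 12% of one standard error.
- **Within arm.** At c = 10 and d = 0.10-0.25, improvement is overstated by 0.25-0.63 points (comparison) and 0.13-0.33 points (ACT).
- **Harm illustration.** If 15% of ACT participants were shifted by +15 and the rest had no change on average, the true difference is 0.15 × 15 = +2.25. It would be seen as +2.13 (d = 0.10), +1.92 (d = 0.25) or +0.39 (d = 1).
- **Home versus clinic ACT.** With both truly at -5 and detection of 25% in one and 10% in the other, the spurious gap is 5.33 - 5.13 = 0.20 points. Which arm gains is unknown.
- **Cross-check by head count.** Losing k of n from one arm only, each g SD worse than those retained, shifts that arm's mean by (k/n)g. For k = 1-3, n = 30 and g = 1-2 this is 0.03-0.20 SD, against a standard error of √(2/30) = 0.26 SD. At an assumed 3% rate, the chance of at least one loss in an arm of 30 is 1 - 0.97³⁰ = 0.60.

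**The case against.** The best reply is that the rule hardly reaches the training sessions. It elaborates a paragraph about distress from the assessments, which take place at Sessions 1 and 8, and the protocol expects no risk from the training itself. What remains is spontaneous disclosure, plus a Study 2 safety question that need not pick up PTSD worsening. This stands, and it is why few people should be affected. It does not close the route, because the trigger is worded generally and staff are in contact with participants during training.

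The ambiguity of the word trial also stands in part. If only training stops, Session 8 could still be offered, and the later PCL-5 contacts do not exclude anyone. A reader might infer that the plan commits to discarding these people's data. The documents do not go that far: no complete-case rule is stated, and the consent form, which may say more about withdrawal, is not in the document reviewed. The text leaves the matter open where one sentence would settle it.

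It is also fair that the size inputs are all assumed, and that the model ignores suicidal or violent intent, which need not track the symptom score. The figures show an order of magnitude and are not evidence about this trial. Finally, the absence of any missing-data rule is a wider gap. This point is a special case of it, but a distinct one, because here a stated rule can stop data collection and no later analysis choice can repair that.

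**Conclusion.** The point holds as a minor, inexpensive improvement. Followed in its more natural sense, the plan can leave participants without a post-treatment CAPS-5 or PCL-5 because they got worse. At 10-25% detection and a cut-off of 10, about 1-2.4 of 100 and 0.7-1.7 of 60 people would be lost, and the between-arm difference would shrink by 0.12-0.30 points on an assumed SD of 10. That is far below sampling error. The true rate is unknown.

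A reader might infer that removing worsened participants biases the trial in favour of ACT. The documents do not support that. With no true effect and equal detection, both arms lose the same kind of people and the difference stays at zero; with a true benefit, the bias is towards no effect. What remains is slightly flattered within-arm change and some under-counting of harm. Detection could differ between home and clinic, but nothing indicates in which direction. The reason to act is that the data cannot be recovered later and the remedy is cheap, not that a large bias is expected.

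**What to change.** Keep referral and stopping of training as they are. Add that referral ends training but not outcome assessment:

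- With consent and no safety objection from the clinician, collect at least the PCL-5, by phone or Qualtrics, at exit or at the planned Session 8 time.
- Add the CAPS-5, by a trained interviewer, where clinically appropriate. It is a structured interview and cannot be delivered through Qualtrics.
- Keep these participants in the 6- and 12-month PCL-5 contacts, timed from their planned end date.
- Analyse them in the arm to which they were randomised, and report discontinuations for worsening by arm.

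**Cost.** One sentence in the procedures and a matching one in the consent form. At 10-25% detection and a cut-off of 10, the extra contacts number 0.97 + 0.68 = 1.65 to 2.43 + 1.69 = 4.12, so roughly 2-4 people and $100-$200 at the $50 session payment. Each CAPS-5 takes 45-60 minutes of existing interviewer time, at most about 4 hours for four people. Some outcomes will still be missing where the clinician objects, and within-arm results may look less favourable.
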